1.2. Objectives

Our aim to test the concurrent validity of the Clarius handheld US devices versus gold-standard device to detect characteristic features of healthy and rheumatic joints (i.e. anatomical structures and vascular flow.

Primary objective:

To determine whether handheld US devices (Clarius HD3 L20 and L15 scanners) B mode are as accurate as gold standard device (GE Logic E9/S8) at visualizing intraarticular synovitis

Secondary objectives:

1. To determine whether handheld US devices (Clarius HD3 L20 and L15 scanners) power Doppler mode are as accurate as gold standard device (GE Logic E9/S8) at detecting intrasynovial signals
2. To determine whether handheld US devices (Clarius HD3 L20 and L15 scanners) B mode are as accurate as gold standard device (GE Logic E9/S8) at visualizing tenosynovitis
3. To determine whether handheld US devices (Clarius HD3 L20 and L15 scanners) power Doppler mode are as accurate as gold standard device (GE Logic E9/S8) at detecting intratendineous signals
4. To determine whether handheld US devices (Clarius HD3 L20 and L15 scanners) B mode are as accurate as gold standard device (GE Logic E9/S8) at visualizing bone erosions
5. To determine whether handheld US devices (Clarius HD3 L20 and L15 scanners) B mode are as accurate as gold standard device (GE Logic E9/S8) at grading intraarticular synovitis
6. To determine whether handheld US devices (Clarius HD3 L20 and L15 scanners) power Doppler mode are as accurate as gold standard device (GE Logic E9/S8) at grading intrasynovial signals
7. To determine whether handheld US devices (Clarius HD3 L20 and L15 scanners) B mode are as accurate as gold standard device (GE Logic E9/S8) at grading bone erosions
8. To determine whether handheld US devices (Clarius HD3 L20 and L15 scanners) power Doppler mode are as accurate as gold standard device (GE Logic E9/S8) at visualizing elementary lesions of enthesitis

9. To determine whether handheld US devices (Clarius HD3 L20 and L15 scanners) power Doppler mode are as accurate as gold standard device (GE Logic E9/S8) at detecting entheseal signals
10. To determine whether handheld US devices (Clarius HD3 L20 and L15 scanners) B-mode are as accurate as gold standard device (GE Logic E9/S8) at detecting trilaminar appearance of the nail plate abnormalities

2. Study Methods

2.1. Trial Design

Multicenter and single arm study (repeating an image collection protocol with hand held US and the gold standard devices for each patient)

2.2. Randomization and Blinding

Study patients will not be randomized to any group. The same anatomical regions will be evaluated with the same ultrasound protocol for each patient included in the study. The scoring of the US images will be done blindly by the principal investigator at OHRI as stated below.

At the central site (OHRI), the research assistant will give a unique identifier number to each image, for a random quality control and for cross referencing whenever needed. The cropped images, as detailed below, will not have the subject ID visible to the PI at the time of reading but will be accessible for the quality control. (read-only access). The research assistant at OHRI is the only site personnel who has the capacity to uncrop the images in the PowerPoint file (password protected files).

Images will not contain any identifiable information such as Date of Birth (DOB) or initials. The US images will be transferred to a PowerPoint file by the research assistant at OHRI in JPEG format. The research assistant will generate an unblinded master list, inaccessible to other site personnel, to link the slide numbers with the patients and scanned anatomical sites and the slide will have no other information on the patient number or ID. For scoring the images by the PI, a random order slide show will be conducted, irrespective of the machine used or the anatomical site or patient assessed, to ensure blindness to data related to the

patient identifiers (The PI will not be blinded to the machine that the image was taken with as the JPEG format that is achieved from different machines are identifiable, but due to the random order scoring, images that belong to the same joint by the different machines are not to be scored consecutively). There will be nine separate powerpoint files, for images of joints, tendons, entheses, nail including power Doppler and gray scale findings; and grey scale file for erosions.

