5.1.2. Secondary Outcomes

5.1.2.1. Joints

After the imaging of all patients is completed, the intraarticular Doppler scoring will be done based on the OMERACT definitions (scales of 0-3) (Table 1):^{5,6}

Power Doppler signal:

Grade 0: no flow in the hypoechoic synovial hyperplasia

Grade 1: up to three single spots signals or up to two confluent spots or one confluent spot plus up to two single spots

Grade 2: vessel signals in less than half of the area of the synovium ($\leq 50\%$)

Grade 3: vessel signals in more than half of the area of the synovium ($> 50\%$)

Also, a lateral view of the 2nd metacarpophalangeal and 5th metatarsophalangeal joints will be recorded in the baseline visit for erosion assessment. Erosions will be described as intra-articular discontinuity of the bony surface seen in 2 perpendicular planes and will be evaluated after the imaging of all patients is completed.

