5.1.2.4. Entheses

After the imaging of all patients is completed, Elementary lesions of enthesitis will be defined and scored as per the GRAPPA US working group's definitions, as used in the multicenter DUET study (Table 2):⁴

All of the elementary lesions will be assessed for their presence or absence. In addition, some of the lesions will also be scored for their severity using a semi-quantitative system (grade 0 to 3). The definitions of each grade are outlined below.

Table-2:Probes/scanners, views and anatomical sites for enthuses assessment

Anatomical site	Views	GE Logic E9/S8	Clarius L15	Clarius L20
Achilles tendon insertions	posterior	X	X	X
Supraspinatus tendon insertions	lateral	X	X	
Triceps tendon insertions	posterior	X	X	
Common extensor tendon origins	lateral	X	X	
Quadriceps tendon insertions	anterior	X	X	
Patellar ligament (origin and insertion)	anterior	X	X	
Plantar fascia insertions	plantar	X	X	
Extensor digitorum tendon insertions at DIP and PIP	dorsal	X		X

The following sonographic enthesal lesions should be scored:

- **Hypoechoicity:** Distinct loss of homogenous fibrillar pattern with relative hypoechoicity compared to the rest of the enthesis after correcting for anisotropy.

Grade 0: Absent

Grade 1: Present

- **Thickening:** Increased thickness of the tendon/ligament at the enthesis compared to its body. Thickness may be difficult to judge and should be suspected when accompanied by other enthesal lesions.

Grade 0: Absent

Grade 1: Present

- **Bone Erosion:** A cortical defect confirmed with a step-down contour defect detected in two planes at the insertion of the tendon/ligament to the bone.

Grade 0: Absent

Grade 1: Present

- **Enthesophyte:** A step-up bony prominence at the normal bone contour. Grade the severity of the enthesophyte based on its length. Although the readers are not expected to measure the length of the enthesis we provided suggested cut off points to guide the grading of the enthesophytes

Grade 0: No enthesophytes

Grade 1: Small enthesophyte

Grade 2: Medium enthesophyte

Grade 3: Large enthesophytes

- **Calcification:** Hyperechoic linear structures detected within the tendon/ligament at the insertion to the bone but with no congruency with the bone.

Grade 0: No calcifications

Grade 1: Punctate hyperechoic area

Grade 2: Linear calcification without acoustic shadow

Grade 3: Egg-shell calcification with posterior acoustic shadow

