- **Doppler Signal:** The presence of positive Doppler signal at the enthesis, confirmed in two perpendicular planes and distinguished from reflection of surface artifacts and nutritional vessel signal.

The intensity of the Doppler signal at the enthesis will be graded using a semi-quantitative score.

Note: We will consider any Doppler signal at the enthesis area including signals appearing beyond 2 mm of the bony cortex.

We will score the intensity of the Doppler signal on a semi quantitative grading system:

Grade 0: No Doppler signal

Grade 1: A single confluent Doppler signal or up to 3 discrete Doppler spots

Grade 2: Doppler signal affecting less than half of the enthesis

Grade 3: Doppler signal covering more than half of the enthesis

In addition, the location of each Doppler signal will be recorded:

Zone 1: ≤ 2 mm from the bone cortex

Zone 2: > 2 mm from the bone cortex

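### Three secondary lesions are defined by two planes, but the random-order reading of individually numbered images makes no provision for the reader to see both planes of a site together

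*SAP*

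**What the plan says.** Three lesion definitions depend on two planes:

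- Joint erosion, SAP 5.1.2.1: "Erosions will be described as intra-articular discontinuity of the bony surface seen in 2 perpendicular planes".
- Entheseal erosion, SAP 5.1.2.4: "A cortical defect confirmed with a step-down contour defect detected in two planes at the insertion". Protocol 4.3 has the same definition.
- Entheseal Doppler, SAP 5.1.2.4: "The presence of positive Doppler signal at the enthesis, confirmed in two perpendicular planes". Protocol 4.3 again matches.

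Scoring is done centrally by the principal investigator from exported still images. SAP 2.2 (and protocol 4.3, under Blinding) says that "the research assistant will give a unique identifier number to each image", and that "a random order slide show will be conducted, irrespective of the machine used or the anatomical site or patient assessed". A separate list exists to "link the slide numbers with the patients and scanned anatomical sites", but the reader cannot use it: "The research assistant will generate an unblinded master list, inaccessible to other site personnel". The slides are divided among nine files, one of them a grey scale file for erosions.

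On image capture, protocol 4.3 makes the longitudinal view standard and saves a transverse view only where the long axis looked abnormal. SAP 5.1.2.1 adds a lateral view of the 2nd MCP and 5th MTP joints, recorded to assess erosion.

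**The concern.** The point is how images reach the reader, not which images are saved. Storing both planes at every site would not help if the two images of one joint or enthesis arrived as unlinked slides, far apart and stripped of patient identity.

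The two-plane rule exists to exclude findings that appear in one plane only; for entheseal Doppler, the definition itself names surface reflection and nutritional vessels as things to be distinguished. A reader who scores each image alone is using a one-plane definition that neither document states. A reader who holds to the written definition has nothing with which to confirm a lesion and would score nearly everything absent. In either case the reported kappa would not describe agreement on the lesion as defined. This touches secondary objectives 4 and 7 (bone erosion, presence and grade), 9 (entheseal Doppler) and the erosion component of 8.

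**Working it through.** **The plan's own figure.** The one computed design figure is the 683 joints in SAP 2.3. With kappa k = 0.61, prevalence p = 0.20, total interval width w = 0.15 and 95% confidence:

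- V = (1−k)[(1−k)(1−2k) + k(2−k)/(2p(1−p))] = 0.39 × [0.39 × (−0.22) + 0.8479/0.32] = 0.9999
- n = 4 × 1.96² × V / w² = 682.87, rounded up to 683.

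This reproduces exactly. It concerns B-mode synovitis, and the present point leaves it unchanged.

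**Passages side by side.**

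| Lesion | Planes required | Source of the second plane | Provision for reading both together |
|---|---|---|---|
| Joint erosion | 2 | Lateral view, 2nd MCP and 5th MTP (SAP 5.1.2.1) | None |
| Entheseal erosion | 2 | Transverse view, only if the long axis is abnormal (protocol 4.3) | None |
| Entheseal Doppler | 2 | As above | None |
| B-mode synovitis (primary) | No such requirement | Not applicable | Not needed |

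Nor does either document send a two-plane finding made at the scan to the reader. The clinical data listed in protocol 4.2 include no ultrasound findings, and image labels carry only site and side.

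**Size for joint erosion.** Assumptions: 30 patients; one dorsal and one lateral image per joint, side and scanner; scanners as in SAP Table 1; only the joints given a lateral view are counted.

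- Joints: 4 per patient × 30 = 120.
- Pairs of views per patient: 2nd MCP, 2 sides × 3 scanners = 6; 5th MTP, 2 sides × 2 scanners = 4; total 10.
- Over 30 patients: 300 pairs, 600 images.

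If each slide holds one image (N = 600 in random order):

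- P(a given pair is adjacent) = 2/N = 2/600 = 0.33%.
- Expected adjacent pairs = 300 × 2/600 = 1.
- Mean separation = (N+1)/3 = 601/3, about 200 slides.

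If each slide holds all views of one site from one scanner, there are 300 slides and every pair is seen together. The documents do not say which layout applies.

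**Size for entheses.** 20 entheses × 30 patients = 600 sites. This is a ceiling, because a second plane exists only where the operator noted an abnormality.

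**Effect on kappa if almost nothing is confirmed.** In the limit where every site is scored absent on both devices, observed and chance agreement are both 1, and kappa = (1−1)/(1−1) is undefined. Close to that limit it rests on a handful of positives and says little.

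**The case against.** The strongest reply is that no passage limits a slide to one image. The image number is described as serving quality control and cross-referencing, whereas the master list works by slide and anatomical site. One slide per site and scanner would fit that text. The random order has a limited stated purpose: to hide patient identity and to keep images of one joint from different machines from being scored one after the other. Nothing says that views from the same scanner must be separated.

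This stands to the extent that a reader might infer that the definitions cannot be applied at all; the documents do not go that far. But the same section speaks of scoring images, numbers them one by one and nowhere groups views, so one image per slide is the natural reading. Two assistants could build different slide sets from this text.

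Other stronger readings are also unsupported:

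- **A single slide show.** There are nine files. This does not remove the point, since the calculation above is for the erosion file alone.
- **The primary outcome is compromised** because SAP Table 1 lists dorsal and lateral views at the 2nd MCP and 5th MTP. SAP 5.1.2.1 gives the lateral views an erosion purpose, and synovitis carries no two-plane rule.
- **All 600 entheses are misread.** Transverse views are conditional, so 600 is an upper limit.
- **The agreement estimate is biased between devices.** Both devices are read under the same rule, and the documents give no basis for saying that single-plane artefact differs between them.

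It is also fair to object that grouping views has a blinding cost; this is taken up under the fix.

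**Conclusion.** The concern holds for secondary outcomes only. The plan defines joint erosion, entheseal erosion and entheseal Doppler by two planes and then describes a reading process that does not provide for the two planes to be seen as one unit. If each slide holds one image, these lesions would not be scored as defined: about 1 of 300 erosion-view pairs would be adjacent by chance, and the reader would not know that the two images belonged together. The scope is 120 joints for erosion and at most 600 entheses for erosion and Doppler. The conclusion rests on the one-image-per-slide reading, which is natural but unstated; if slides are in fact to be grouped by site, the remaining defect is that the plan does not say so. The primary kappa and its sample size are unaffected. The change should be made before images are read.

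**What to change.** In protocol 4.3 and SAP 2.2:

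- For the erosion file and the entheseal grey scale and Doppler files, make the reading unit one slide per anatomical site per device, showing both saved planes: dorsal and lateral for the 2nd MCP and 5th MTP, longitudinal and transverse for entheses.
- Randomise slide order within each file, keep devices on separate slides, and record one score per slide.
- Leave the synovitis file as it is. Add a footnote to SAP Table 1 that the lateral views serve erosion only, in line with SAP 5.1.2.1.
- Do not score a slide as the highest grade over its views. That would favour positive scores wherever more views happened to be saved.

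The cost is a wording change and a different slide layout by the same research assistant, with fewer slides to read and no new images. The real downside is at the entheses: because a transverse view is saved only when the long axis looks abnormal, a grouped slide tells the reader that the operator noted something at that site with that device. The cue also reaches the other lesions scored from the same entheseal slides. It should not arise for the 2nd MCP and 5th MTP erosion slides, where both views are planned for every patient. Limiting grouping to these files confines the cost to secondary outcomes, and the SAP should state it as a limitation.

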4.0 Approaches and Methods

Number of arms: single arm (repeating an image collection protocol with hand held US and the gold standard devices for each patient)

Blinding: The scoring of the US images will be done in a blinded fashion. The de-identified images from different patients and different scanners will be pooled to ensure the principle investigators (PIs) blindness to both the patients' clinical findings and the scores of other imaging modality.

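### The single reader can see which machine made each image, the plan does little to reduce this, and simple random order does not keep same-joint images apart as stated

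*SAP*

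**What the plan says.** Protocol 4.0 states that "The scoring of the US images will be done in a blinded fashion" and gives the aim as "blindness to both the patients' clinical findings and the scores of other imaging modality". SAP 2.2 opens in the same way: "The scoring of the US images will be done blindly by the principal investigator at OHRI as stated below". SAP 2.4 also describes the interim comparison as following blinded scoring.

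The detail is in SAP 2.2, with the same text in Protocol 4.3. Cropping is described as keeping the subject ID from the reader. For the order of reading, "a random order slide show will be conducted, irrespective of the machine used or the anatomical site or patient assessed". A parenthesis then adds that "The PI will not be blinded to the machine that the image was taken with", because the exported JPEGs can be told apart, but that "due to the random order scoring, images that belong to the same joint by the different machines are not to be scored consecutively". The scoring is organised in several decks: "There will be nine separate powerpoint files".

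Neither document describes a constraint on the shuffle, a minimum gap between images of the same joint, an interval between sittings, removal of machine-specific overlays, a second reader or a repeat reading.

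**The concern.** The machine is the factor under comparison, and it is the one attribute the reader is told. The same person scores both members of every pair. An expectation about the handheld can therefore enter borderline calls on one side of the comparison and pass straight into the primary kappa. More joints would not reveal or remove such a shift.

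The remaining safeguard is separation of same-joint images, so that the second score is not matched to the first. The plan treats separation as a consequence of random order. If random order does not produce it, the protection of the paired score is weaker than described.

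Two decisions rest on these readings: the final comparison with kappa 0.61 (SAP 2.3) and the interim rule of kappa above 0.40 that lets subsequent studies start (SAP 2.4).

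**Working it through.** **The plan's own figure.** SAP 2.3 gives kappa k = 0.61, prevalence p = 0.20, confidence interval width 0.15 and 683 joints; SAP 3.1 gives 95% intervals.

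- n × Var = (1−k)[(1−k)(1−2k) + k(2−k)/(2p(1−p))] = 0.39 × [0.39 × (−0.22) + 0.8479/0.32] = 0.99992.
- n = (2 × 1.96/0.15)² × 0.99992 = 682.9, so 683 joints.

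The figure reproduces with 0.15 as the full width. It is not affected by this point. The documents give no figure for the ordering rule.

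**Size of the greyscale joint file** (SAP 5.1.1, Table 1; both sides counted; one B-mode image per joint and probe assumed).

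- GE: 24 joints per patient.
- Clarius L15: 2nd MCP, wrist, elbow, shoulder, knee and ankle = 6 × 2 = 12.
- Clarius L20: 2nd and 3rd MCP, two PIP, two DIP, wrist and 5th MTP = 8 × 2 = 16.
- Slides for 30 patients: 30 × (24 + 28) = 1,560. GE-Clarius same-joint pairs: 30 × 28 = 840.

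**Adjacency under a simple shuffle.** A given pair is adjacent with probability 2/N, so the expected number is E = 2M/N for M pairs, and P(at least one) ≈ 1 − exp(−E).

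- E = 2 × 840/1,560 = 1.08; P ≈ 1 − exp(−1.08) = 0.66. A simulation of 4,000 shuffles also gave 66%.
- Near pairs in simulation: about 5.4 within 5 slides, 10.8 within 10 and 21 within 20.
- If L15 and L20 also count as different machines, there are 960 pairs: E = 1.23, P = 0.71.
- Interim file, 10 patients: 2 × 280/520 = 1.08, the same value.
- Other decks, on the same assumption: tendons 2 × 120/240 = 1.0; nails 2 × 60/120 = 1.0; entheses 2 × 660/1,260 = 1.05.

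**Effect of adjacency on kappa.** At k = 0.61 and p = 0.20, chance agreement is 0.04 + 0.64 = 0.68 and observed agreement is 0.68 + 0.61 × 0.32 = 0.8752, so 12.48% of pairs are discordant. Turning one discordant pair in 720 into a concordant one adds (1/720)/0.32 = 0.0043. Expected shift: 1.08 × 0.1248 × 0.0043 = 0.0006.

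**Effect of knowing the machine (illustration; the bias rate is assumed).** Starting cells: both positive 0.1376; GE only 0.0624; handheld only 0.0624; both negative 0.7376. The reader turns 10% or 20% of handheld positives into negatives. Handheld prevalence becomes 0.18 or 0.16, and chance agreement 0.692 or 0.704.

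| Which handheld positives are lost | 10% | 20% |
|---|---|---|
| At random | (0.8677 − 0.692)/0.308 = 0.57 | (0.8602 − 0.704)/0.296 = 0.53 |
| Only handheld-positive, GE-negative joints | (0.8952 − 0.692)/0.308 = 0.66 | (0.9152 − 0.704)/0.296 = 0.71 |

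The shifts run from about −0.08 to +0.10. The planned half-width of the interval is 0.15/2 = 0.075.

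**The case against.** - **The exception is disclosed.** A reader might infer that the documents contradict themselves, or conceal that the machine is visible. They do not support that. Protocol 4.0 lists what the blinding covers and the machine is not on the list; SAP 2.2 qualifies its opening sentence by referring to the detail below it, and that detail states the exception and the reason. This stands. What remains is a known exposure with little done to reduce it.
- **Adjacency is trivial in size.** About 1 pair in 840 is affected, and slides carry no patient ID, so the reader would first have to recognise that two images show the same joint. This stands too. A reader might infer that failed separation distorts the primary kappa; the arithmetic puts the shift below 0.001. The sentence in the plan is still inaccurate as a description of what a simple shuffle does.
- **The sign of the bias is unknown.** A reader might infer that knowing the machine must count against the handheld. That holds if positives are lost at random. If the lost calls are the doubtful ones that GE did not show, agreement rises. The documents support neither a direction nor a rate.
- **Full image standardisation could do harm.** Doppler location is scored as within or beyond 2 mm of the cortex (Protocol 4.3, SAP 5.1.2.4), so removing every depth scale would remove the distance reference. Synovitis and several enthesis lesions are judged by echogenicity, so remapping greyscale could change what is graded. This stands and limits the remedy to material outside the tissue window.

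**Conclusion.** The concern holds in a limited form. The only reader knows the machine for every image; the plan says so but goes no further than hiding the subject ID and shuffling the slides. The shuffle does not deliver the stated separation: 1.08 adjacent GE-Clarius pairs are expected in the joint file, with a 66% chance of at least one. That result assumes one image per joint and probe. Protocol 4.3 sets one as a minimum and adds transverse views for abnormal findings, but the expectation stays at about one or more per file.

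The adjacency failure has a negligible effect on kappa. Knowledge of the machine is the part that matters. Its size cannot be derived from the documents; the range of 0.53 to 0.71 around 0.61 only shows that a modest assumed bias could move the primary result across the plan's criterion in either direction. This is an inexpensive improvement to the reading procedure. It is not evidence that the result will be biased, and the 683-joint calculation is unchanged.

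**What to change.** In Protocol 4.3 and SAP 2.2:

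1. **Cropping.** Extend the existing cropping to remove logos, text and frame outside the tissue window on every image. Keep a distance reference in one neutral format so that the 2 mm Doppler zones can still be scored. Leave greyscale and Doppler colours as exported.
2. **Order.** Replace the simple shuffle with a constrained one. For each joint, randomly allocate the GE image to one of two reading sittings and the handheld image or images to the other, with the interval between sittings stated in advance. Apply this at the interim and the final reading. GE-handheld adjacency within a sitting is then zero by construction, and drift of the reader over time is balanced between machines. For the joint file, each sitting averages 1,560/2 = 780 slides, so a sitting may have to be a block of several sessions.
3. **Wording.** In Protocol 4.0, SAP 2.2 and SAP 2.4, state that reading is masked to patient, clinical findings and the paired score, but not fully to machine.

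Cost: some deck preparation by the research assistant who already crops the images and builds the files, and a longer reading schedule. No extra patients or scans are needed. Image texture may still reveal the scanner, so masking of the machine stays partial and should be reported as such.
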